5.7.2. Other measures

Cost methodology To determine costs, we will collect data to capture all relevant direct (e.g. equipment) and indirect (e.g. administrative), fixed (or 'start-up') and variable (or 'recurring') costs related to the intervention and control groups (Table 4). Costs will be differentiated by intervention component (e.g. clinic-based counseling versus remote booster sessions) and by booster session mode of delivery (i.e. live booster versus tech booster, and between SMS and IVR tech boosters). The data collection for costs and the analyses will be conducted using Excel-based worksheets previously developed by [name] and UCSF teams for related settings.^{155,156} The Ugandan project coordinator will collect these costs in years 2-4 with consultation from [name]. We will estimate the marginal cost per unhealthy drinker (i.e. the change in the total cost of the intervention when one additional person is added to the program), overall and by study arm.

Table 4. Cost data collection

Cost category	Description	Source
Personnel – Ongoing	Personnel needed to conduct the in-person counseling, the live and tech boosters, to train patients to receive and respond to the tech boosters, to respond to queries by patients receiving the tech boosters, and to enter new patients and their information into the tech booster system.	MUST contracts and grants office
Personnel – Start up	Personnel needed to set up the tech booster system	As above
Space -- Ongoing	Space needed at the ISS clinic for each intervention arm	ISS Clinic
Equipment/services – Start up	Cell phones, computer and internet needed for setting up and maintaining the tech booster system, tech booster call costs, air time reimbursement,	MUST contracts and grants office

	internet time, office supplies, furniture, data storage.	
Organizational	Costs of meetings and trainings conducted in the clinic	ISS Clinic
Client time	Client time for receiving in-person components of intervention, plus training on the 2-way tech boosters	Counselor records

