2.1. Specific Aims

The goal of this study is to estimate the uptake and acceptability, efficacy, and cost of methods of delivery of an intervention to reduce unhealthy drinking and HIV viral failure in a randomized controlled trial (RCT) among persons in HIV care in rural Uganda (n=270). The arms will be (1) in-person counseling during 2 quarterly clinic visits plus live booster phone calls every three weeks in the interim; (2) in-person counseling during 2 quarterly clinic visits plus tech (choice of SMS or IVR) boosters once to twice weekly in the interim; and (3) standard of care (SOC) control (brief unstructured advice, with a wait-listed intervention). We will measure outcomes as follows:

- a) **Outcome 1 is the efficacy** of an intervention to reduce unhealthy drinking and reduce HIV viral failure. This will be measured at nine months using self-report (number of drinking days in the past 21) and phosphatidylethanol (PEth), an alcohol biomarker, and viral suppression.
- b) **Outcome 2 is the uptake and acceptability** of an intervention to reduce unhealthy drinking and reduce HIV viral failure: We will examine the completion rates of the live and tech boosters, conduct post-intervention satisfaction surveys, and conduct qualitative interviews among a subsample of study participants (n=25-30) to determine acceptability and experiences with the three study arms.
- c) **Outcome 3 is the estimate of the cost of the delivery methods** of an intervention to reduce unhealthy drinking and reduce HIV viral failure: We will collect data to estimate the cost of each study arm and each mode of tech booster delivery to the patients and the clinic, including both start-up costs (e.g. initial fixed costs in tech system set-up) and maintenance costs (e.g. ongoing/recurring costs such as SMS/IVR fees, and personnel costs).

This study will be conducted in a large rural Ugandan clinic where we have 10 years of collaborative alcohol/HIV research experience. The end products of this study will be the comparisons of key outcomes to estimate effect sizes and inform the design of a future large-scale trial. The long-term aim is to implement interventions that reduce alcohol use and improve HIV outcomes feasibly and at low cost in low resource settings.

3. Background and rationale

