For those in the technology booster arm, the counselor will obtain information for the tailoring variables during the in-person session, and will enter them into the technology program interface. The counselor will engage in demonstrations of the SMS and IVR boosters and a discussion of the pros and cons of each, to help participants decide which they prefer, based on their level of literacy, need for confidentiality, and other considerations. After the choice is made, the counselor will provide further training on using SMS or IVR, entering a PIN# to obtain the messages, and responding to the questions. As was effective in increasing engagement in previous tech interventions,¹²⁶ the counselor will send a test SMS or IVR message to Arm 2 participants and watch them enter the PIN# and access and respond to the message, assisting and sending another message as needed. The counselor will also show those choosing SMS how to delete the SMS from their phones after the session. The data manager will monitor SMS/IVR session completion; if there is a 3-week interval with no tech booster session interaction, the data manager will alert the counselor who will call the participant and his/her contacts to verify if the cell phone number is still correct. Participants in both booster arms will receive reminders before they are due for their 2nd in-person counseling session, which will be scheduled to coincide with their next clinic visit.

5.4.2. Intervention delivery in Arm 3

Participants randomized to Arm 3 (SOC) will have no contact with the study counselor for the duration of the trial (9 months). However, at their 9-month study visit, and at the end of their study participation as randomized, they will be offered the intervention and given a choice of the delivery method for the booster sessions. Although the study counselor will deliver the intervention at this time point, we will not collect intervention data associated with this group.

Table 2. RCT study visit and intervention schedule

Study enrollment, baseline questionnaire, DBS collection, and randomization			
Month 0	Arm 1: In-person counseling plus live booster (n=90)	Arm 2: In-person counseling plus tech booster (n=90)	Arm 3: SOC control (n=90)
	In-person counseling session	In-person counseling + tech training	Standard care
Months 1-3	Live booster (every 3 weeks over 12 weeks)	Tech booster (1X to 2x/week over 12 weeks)	---

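### Table 4's client-time row leaves out participant time on live calls and SMS/IVR sessions, so the patient-side cost contrast between booster modes is incomplete

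*Combined protocol and SAP*

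**What the plan says.** Section 2.1, Outcome 3, sets the perspective: the study will "estimate the cost of each study arm and each mode of tech booster delivery to the patients and the clinic". Section 5.7.2 sets the breakdown: "Costs will be differentiated by intervention component (e.g. clinic-based counseling versus remote booster sessions") and also "by booster session mode of delivery (i.e. live booster versus tech booster, and between SMS and IVR tech boosters"). The cost estimand follows: "We will estimate the marginal cost per unhealthy drinker", overall and by arm.

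Table 4 then lists the data to be collected. Its one client-time row reads "Client time for receiving in-person components of intervention, plus training on the 2-way tech boosters", with counselor records as the source. Other rows cover staff for the live and tech boosters, tech call costs and air time reimbursement.

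The Table 2 schedule gives "Live booster (every 3 weeks over 12 weeks") for Arm 1 and "Tech booster (1X to 2x/week over 12 weeks") for Arm 2. Both arms have the same two in-person sessions, and Arm 2 also has tech training at the first.

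**The concern.** Arms 1 and 2 are built to differ in how boosters are delivered, and the client-time row stops short of the boosters. Section 6.2 expects no extra phone charges for participants, because incoming calls and messages are free and the study pre-loads air time for SMS replies. Time is therefore the main cost left on the patient side.

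The introduction (Section 2) hypothesises that automated delivery carries low burden and cost for patients as well as providers, and it describes live boosters as demanding of time. The background (Section 3) says the preliminary cost data will help choose which interventions enter a larger trial. If the row is followed as written, the patient half of that hypothesis is judged without the time participants spend on the boosters.

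**Working it through.** The documents give no client-time figure, so there is none to reproduce. The check has two parts.

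**1. What Table 4 lists for client time, by arm**

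| Client-time item | Arm 1 (live) | Arm 2 (tech) | In Table 4? |
|---|---|---|---|
| Two in-person sessions | yes | yes | yes |
| Tech-booster training | no | yes | yes |
| Time on live calls | yes | no | no |
| Time on SMS/IVR sessions | no | yes | no |

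The in-person sessions cancel by design. The listed difference, Arm 2 minus Arm 1, is therefore the training time T, which cannot be negative. Between SMS and IVR, no booster-session time is listed.

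**2. How much is left out**

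Counts from Table 2, with 90 participants per arm and every session delivered:
- Live calls: 12 weeks / 3 = 4 per person; 4 x 90 = 360 in Arm 1.
- Tech sessions: 12 x 1 = 12 to 12 x 2 = 24 per person; 12 x 90 = 1,080 to 24 x 90 = 2,160 in Arm 2.

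Durations are not in the documents. I assume 5-20 minutes per live call, 1-5 minutes per tech session, and T = 15 minutes.
- Arm 1 booster time: 4 x 5 = 20 to 4 x 20 = 80 minutes per person.
- Arm 2 booster time: 12 x 1 = 12 to 24 x 5 = 120 minutes per person.
- Arm 2 minus Arm 1, boosters only: 12 - 80 = -68 to 120 - 20 = +100 minutes.
- With training added: 15 - 68 = -53 to 15 + 100 = +115 minutes, where Table 4 alone would give +15.

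The sign stays open for other training times. T = 5 gives -63 to +105, and T = 30 gives -38 to +130.

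Uptake matters too. If half the sessions were completed in each arm (50% is the example completion level in the uptake power statement of Section 5.9.1), the booster-only range halves to -34 to +50 minutes. With T = 15 it is -19 to +65. The range narrows but still spans zero.

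**The case against.** The best defence is that Table 4 is a short summary. The sentence introducing it commits to capturing every relevant direct, indirect, fixed and variable cost, and the costing worksheets and the counselor's call record form are not in the documents. Call duration may already be recorded. Section 5.4.1 has attempted and completed calls logged, and Section 5.7.1 says the technology databases record SMS and IVR interactions. On this view, nothing says booster time is excluded or valued at zero.

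Part of this stands. A reader might infer that the plan sets booster time to zero, or that the patient-side contrast is wrong by construction. The documents support neither. The row is silent on booster time, and the direction of any error depends on durations and uptake that are not given. Many plausible values put more patient time in Arm 2, the same direction that training alone would show. The count of 4 calls is not firm either: boosters fall between the two in-person sessions, so a week-12 call could coincide with the month-3 session and leave 3.

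It does not remove the point. The general commitment refers to Table 4 for its content, and the row states what is counted. Its named source, counselor records, would not obviously hold a participant's time on automated sessions. Nowhere do the documents say that session duration is recorded or used for costing.

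**Conclusion.** The point holds as an incompleteness in the patient-side cost data. The client-time row does not deliver what Outcome 3 and the planned breakdown promise. It omits about 4 live calls per person in Arm 1 and 12 to 24 tech sessions per person in Arm 2. The one difference it names between these arms is charged to Arm 2. The resulting contrast may be wrong in size or sign, and neither can be settled from the documents. The minute ranges above rest on assumed durations and, unless stated otherwise, full uptake.

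A reader might also infer that the whole live-versus-tech cost comparison is compromised. It is not: booster staff, call costs and air time are listed, so the clinic-side comparison stands. The efficacy analyses are untouched. Cost is the third outcome of a study that Section 5.9.1 calls a pilot, and no formal test of patient time is planned. This is a worthwhile improvement of modest priority.

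**What to change.** Extend the client-time row of Table 4 to completed booster sessions, with a source for each mode:
- **Live calls:** a call-duration field on the counselor's call record.
- **IVR:** logged call length, if the platform stores it (the documents do not say).
- **SMS:** number of completed sessions times a measured or stated time per session. Reply timestamps should not be used, because participants can answer when they choose (Table 1 rates this flexibility high for SMS) and the gap would reflect delay, not active time.

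Report the result by arm and by SMS/IVR, and vary the per-session assumption. Reconcile the tech schedule first: Section 4 gives twice weekly, while Sections 2.1 and 5.3 and Table 2 give once to twice weekly.

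The alternative is to state that participant time on boosters is excluded and to narrow the patient-cost claim in Outcome 3 accordingly.

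The cost of extending the row is one extra form field, one data extract and minor analysis work, plus a small timing exercise if the SMS per-session time is measured and not assumed. The duration field needs to be in place before calls are made, since call length may not be recoverable afterwards.

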5.8. Data management

We will build on our previous data collection, tracking, and specimen bar-coding systems used in Uganda. The surveys will be RA-administered using the RedCap program for offline data collection on laptop computers. The field coordinator will observe 10% of the quantitative surveys and qualitative IDIs to assure that data are being collected in a systematic, unbiased method. The electronic data will be uploaded daily and monitored by the UCSF statistician who will check all data for completeness and range monthly. Discrepancies will be investigated and resolved by the UCSF statistician and the Uganda data manager.

5.9. Statistical analysis plan

The analyses below will provide effect sizes to inform a future large-scale trial.

5.9.1. Primary analyses

Efficacy analyses

The analysis for primary outcome variable 1 (alcohol reduction) will measure the number of drinking days (of the prior 21) at six months and nine months, in pairwise comparisons of the study arms, controlling for baseline days drinking (of the prior 21).¹⁴⁹ The analyses will be conducted as intention-to-treat, and we will use Poisson or negative binomial regression for the count data, i.e. the number of drinking days at 6 and 9 months, controlling for baseline days drinking. The PEth level will be transformed to log10 PEth before analyses, based on PEth's highly skewed distribution and we will use linear regression for this outcome.

The analysis for primary outcome variable 2 (HIV viral suppression) will use logistic regression to compare the proportions with viral load<500 copies/ml, controlling for baseline viral load. We will adjust these analyses for baseline characteristics that exhibit imbalance between groups (based on a p-value ≤ 0.1 in comparisons of potential confounders listed in Table 3).

Secondary outcomes: Other exploratory outcomes will include CD4 cell count and ART adherence.

Missing data We will evaluate differences in baseline characteristics between those lost to follow-up versus those who are retained.¹⁵² If it is reasonable to assume that data are missing at random, multiple imputation methods will be applied to account for the missing data.^{152,153} We will also consider pattern mixture models,¹⁵⁴ which are applicable when the data are missing not at random.

Statistical power: With a sample size of 90 in each arm, assuming 90% 9-month retention, using a simplifying t-test for power calculations, we will have 80% power to detect a difference in the number of drinking days in the prior 21 between two study arms at nine months of ≥ 2.4 days, i.e. nearly 1 fewer day per week, as statistically significant ($\alpha=0.05$) assuming that the mean number of drinking days in the prior 21 in the control group is 7 (standard deviation is 5.5, based on prior data). Given that this is a pilot study we will not adjust for multiple comparisons.

Booster uptake and satisfaction analyses

Analyses We will calculate 95% confidence intervals for the outcomes listed above. We will conduct preliminary tests of whether the mean completion proportions and satisfaction scores differ by booster arm (live versus tech) by conducting 2-sample tests (t-test or Mann-Whitney).

Statistical power We will have 80% power to detect a difference of completion proportion of 11% or greater if the mean completion in one group is 50%. Power will be greater for mean proportions completing closer to 1.

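### The primary analysis of drinking days names two count models but no standard error: default Poisson would inflate false positives to roughly 20–36%, and default negative binomial usually gives up some power

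*Combined protocol and SAP*

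**What the plan says.** Section 5.9.1 (Efficacy analyses) defines the first primary analysis as one that "will measure the number of drinking days (of the prior 21) at six months and nine months", compared pairwise between arms by intention to treat and "controlling for baseline days drinking (of the prior 21"). On the model it says only "we will use Poisson or negative binomial regression for the count data". It names no rule for choosing between the two, no robust or overdispersion-scaled standard error, and no form for the baseline term.

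The power paragraph in the same section works "using a simplifying t-test for power calculations": "With a sample size of 90 in each arm, assuming 90% 9-month retention", "we will have 80% power to detect a difference in the number of drinking days in the prior 21" of "≥ 2.4 days, i.e. nearly 1 fewer day per week", where "the mean number of drinking days in the prior 21 in the control group is 7" and the SD is 5.5. No power is given under either count model. The section plans no difference in mean days from the regression, although the target is in days.

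**The concern.** Both models tie the variance to the mean. Poisson sets them equal, which the plan's own SD contradicts. The negative binomial lets the variance grow with the square of the mean, a poor description of an outcome confined to 0–21. With model-based standard errors, a wrong variance function goes straight into the test.

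Three things are at stake.
- **Error rate.** One of the two permitted options has a false-positive rate several times the nominal 5%.
- **Sensitivity.** The other can be less sensitive than simple alternatives on the same data. Section 5.9.2 treats self-report and PEth as conclusive when both or neither reach significance, so a weak self-report test can create avoidable discordance.
- **Scale.** Section 5.9 says the analyses are to supply effect sizes for a larger trial. The target is in days, but both permitted models return a rate ratio.

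**Working it through.** **1. Inputs from section 5.9.1.** 90 per arm × 0.90 retained = 81 analysed; control mean 7; SD 5.5; difference 2.4 (so 4.6 in the other arm); α = 0.05. Sidedness is not stated; two-sided is assumed.

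**2. The plan's own figure.** SE = 5.5 × √(2/81) = 0.864; 2.4/0.864 = 2.777; power = Φ(2.777 − 1.960) = 79.3% (78.8% by noncentral t). The stated 80% reproduces.

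**3. Poisson, model-based SE.** Variance/mean = 5.5²/7 = 30.25/7 = 4.32. The standard error is too small by √4.32 = 2.08, so with no baseline correlation the false-positive rate is about 2 × [1 − Φ(1.96/2.08)] = 35%. If baseline explains a share r² of the variance, 4.32 becomes 4.32 × (1 − r²); at r = 0.7 this is 2.20 and the rate is about 19%. Simulation (beta-binomial on 21 days, 2,004 trials per scenario, correlation 0 to 0.7) gave 36% falling to 20%.

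**4. Why the negative binomial loses power.** Its variance is m + m²/k. Matching mean 7 and SD 5.5 needs k = 49/(30.25 − 7) = 2.11, which puts 4.6% of people at zero days. A beta-binomial with the same mean and SD has intraclass ρ = [30.25/(21 × ⅓ × ⅔) − 1]/20 = 0.274 and 10.2% at zero. Maximum likelihood absorbs the different shape by lowering k: fitted to that beta-binomial with no covariate, k = 1.51, so the fitted variance is 7 + 49/1.51 = 39.5 rather than 30.25. The standard error is then too large by √(39.5/30.25) = 1.14. In simulation the type I error of the model-based negative binomial was 3.1–4.1% at correlations 0 to 0.5 and 5.4% at 0.7.

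**5. Power at 2.4 days, 81 per arm.** All runs use beta-binomial control data with mean 7 and SD 5.5.

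(a) Shift of the whole distribution to mean 4.6, linear baseline, 2,004 trials (Monte Carlo SE about 0.9 points at 80%). The comparator is a logit-link model for days/21 with a scaled SE. Where both SEs were tabulated, the sandwich version was within 0.4 points of it.

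| Baseline correlation | 0 | 0.3 | 0.5 | 0.7 |
|---|---|---|---|---|
| Same ρ in both arms: negative binomial | 76.6 | 81.2 | 88.4 | 96.4 |
| Same ρ: logit, days/21 | 82.7 | 85.2 | 91.1 | 97.6 |
| Same SD in both arms: negative binomial | 67.5 | 75.3 | 86.1 | 96.1 |
| Same SD: logit, days/21 | 77.2 | 80.6 | 86.5 | 95.6 |

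The loss is 6.1, 4.0, 2.7 and 1.2 points in the first pair, and 9.7, 5.3, 0.4 and −0.5 in the second. With baseline entered as log(days + 1) it goes as low as −2.1.

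(b) By mechanism, model-based negative binomial against logit days/21 with sandwich SE, two settings each, 500 trials:
- proportional cut in each person's days: 90 vs 95% and 94 vs 99%;
- shift: 87 vs 90% and 96 vs 97%;
- some participants stop drinking: 68 vs 84% and 72 vs 87%, with the unadjusted t-test at 78–79%.

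A separate run (800 trials, baseline correlation 0.43 and 0.60) gave 90.1 vs 95.5% and 93.8 vs 98.5% for the proportional cut, and 64.5 vs 82.4% and 71.6 vs 88.4% for stopping. The sandwich model's type I error was 5.9% and 5.6% there.

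(c) If the data are negative binomial capped at 21 (correlation 0): 90.1 vs 90.5%, essentially no loss.

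**6. Is the 21-day ceiling the cause?** ANCOVA on days and Poisson with robust SE both ignore the ceiling. Both came within about 2 points of the logit model. The negative binomial with robust SE was within 1.5 points of it in all eight scenarios of (a), but still trailed by 3–10 points in proportional-cut and stopping scenarios.

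**The case against.** The strongest reply is that a competent analyst would see variance/mean of 4.3, discard plain Poisson and fit the negative binomial, whose type I error is acceptable. On this view the plan openly calls its t-test a simplification, a rate ratio is a legitimate effect size, and this is a pilot. Much of that stands. The 80% reproduces, and with common dispersion and a baseline correlation of 0.3 or more the negative binomial still reaches 81–96% at 2.4 days. It does not follow that the SAP should leave the model and standard error open: the Poisson option remains on the page, and the choice would be made with data in hand.

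Some stronger readings are tempting and should not be drawn.
- *The ceiling is what costs power.* Step 6 rules this out: unbounded models with a suitable standard error do about as well.
- *The plan loses a fixed number of points, or cannot reach 80%.* The documents give no distribution shape, intervention-arm SD, baseline correlation or mechanism. The loss ranges from slightly negative to about 18 points over the cases above.
- *The model predicts impossible values.* Fitted means above 21 at a baseline of 21 days occurred in about half of samples at correlation 0.60, but at 0.43 the fitted mean was about 15. Linear entry of baseline is itself an assumption, and the arm comparison is not invalidated.

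**Conclusion.** The point holds as a gap in specification that should be closed before analysis.

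The firmest part follows from the plan's own mean and SD: model-based Poisson would give a false-positive rate of roughly 20–36%, depending on how much baseline explains. The documents do not say that model-based errors will be used; they are silent, and model-based is what the wording yields if nothing is added.

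The power part is directional. Model-based negative binomial is usually weaker than a baseline-adjusted model with sandwich errors at 2.4 days. The loss is about 0–5 points for a shift or proportional reduction (6–10 if baseline is uninformative). It is about 15 points (15–18 in the runs above) if the effect comes from some participants stopping; there the planned model falls below the unadjusted t-test behind the stated 80%. These sizes are conditional on assumed shape, correlation and mechanism. The loss is near zero for capped negative binomial data, and robust errors on the negative binomial recover part or most of it. The cause is the variance function and the type of standard error.

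**What to change.** Replace the model sentence in section 5.9.1 with one prespecified primary model: logit-link regression of days/21 on arm and baseline days, with sandwich standard errors, for each pairwise comparison at six and nine months. Report the marginal difference in mean days with its 95% CI, which puts the result on the scale of the 2.4-day target. ANCOVA on days performs the same and is an acceptable alternative if a simpler model is preferred; name one of the two. State the form of the baseline term. Keep the negative binomial rate ratio as a sensitivity analysis, and remove Poisson with model-based errors as an option.

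The cost is SAP wording only, with no change to data collection or sample size. In the scenarios tried the replacement was never materially worse than the negative binomial, and its type I error was between about 5% and 6%. The one downside is that the rate ratio moves to a supportive table.
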